#### 6.2 Efficacy Variables

The following efficacy variables will be used for assessment of the secondary endpoints in this study (for secondary efficacy endpoints, refer to Section 3.2.2, for times of assessment, refer to Table 3).

- VAS (see Appendix 11.3) for assessment of worst leg pain and worst back pain
- ODI (see Appendix 11.4) for assessment of functional disability
- FNS or SLR test, sensation, muscle strength, and deep tendon reflex for assessment of neurological status
- Record of occurrence of post-treatment surgery for lumbar disc herniation at the same level of administration of the investigational drug up to Week 26 including patients who discontinued from the study.

#### 6.3 Demographics and Baseline Characteristics

#### 6.3.1 Patient Demography

For patient demography the following will be documented:

- Year of birth
- Age
- Gender
- Race
- Smoking history
- Occupation (Heavy labor/Light labor)

#### 6.3.2 Disease History

For disease history the following will be documented:

- Lumbar disc herniation (L1–L2, L2–L3, L3–L4, L4–L5, or L5–S1) "protrusion type" or "extrusion type" in the posterior lateral or central location as assessed by MRI
- A positive FNS ≤70° (L1–L2, L2–L3, or L3–L4) or SLR ≤70° (L4–L5 or L5–S1) on the symptomatic side
- No improvement from adequate conservative treatment prior to the time of informed consent
- Sciatica or anterior thigh pain/femoral neuropathy in either leg prior to the time of informed consent
- A worse leg pain by VAS ≥30 mm during the past 24 hours at the time of informed consent

# 6.3.3 Medical History

For documentation of the medical history, any previous and concomitant diseases within the last 26 weeks and any significant medical history occurring before the time of informed consent will be documented.

The medical history will be obtained by interviewing the patient or by inspecting his/her medical records.

For coding of medical history, see Section 9.4.

#### 6.3.4 Previous and Concomitant Medications/Therapies

Previous and concomitant medication/therapy will be documented as described in Section 5.7 and Section 5.8. For coding of previous and concomitant medications/therapies, see Section 9.4.

#### 7 STUDY CONDUCT

#### 7.1 Schedule of Procedures

Each patient will be asked to complete 6 study visits including a screening evaluation:

- Screening visit
- Treatment Day 0
- Evaluation period/Follow-up visits at Week 1, Week 6, Week 13, and Week 26
- Patients terminating the study early will be asked to complete a discontinuation visit.

Table 3:         Schedule of Assessments and Procedures								
Observation Period	Before 4 Weeks (Day -28 to Day 0)	Treatment	Day 0	Week 1	Week 6	Week 13	Week 26	Upon Discontinuation
	Outpatient a							Upon Disc
Observation / Examination Items	Screening Period	Evaluation Period/ Evaluation Period/ Follow-up						
	Visit 1	Visi	it 2	Visit 3	Visit 4	Visit 5	Visit 6	
Permissible lag time for				±3D	±14D	±14D	±14D	+14D
observation/examination Verify conformance with entry criteria Obtain informed consent	Х							
Patient characteristics	Х							
Serum/urine pregnancy test b	Х	Х						
Patient enrollment		Х						
Administration of the investigational drug		▼						
Pain assessment by patients (VAS)	Х	Х		Х	Х	Х	Х	Х
ODI		Х		Х	Х	Х	Х	Х
Physical examination	Х	Х						
Neurological examination	Х			Х	Х	Х	Х	Х
Imaging (X-ray, MRI) c	Х				Х	Х	Х	Х
Vital signs	Х	Х	Х	Х	Х	Х		Х
Laboratory tests	X			Х	Х	Х		X
Serum anti-SI-6603 antibody d		Х				Х	Х	Х
Concomitant drug/therapy								→ X
AE/SAE								> x
Record occurrence of lumbar surgery e								⇒ X

#### ~ . **.** . . .

. .

 $\mathbf{V}$ =Administration of the investigational drug; D=day; X=Essential examination AE=Adverse event; MRI=Magnetic Resonance Imaging; ODI=Oswestry Disability Index; SAE=Serious adverse event; VAS=Visual Analog Scale

#### **Procedures by Visit** 7.2

Visits should occur within the time indicated for each scheduled visit. All times should

<sup>*a* Hospitalization on the day at administration is allowed if it is required by the site.

<sup>b Serum pregnancy test will be performed at Screening, and urine pregnancy test will be performed at *Visit 2 before administration of the investigational drug.* 

<sup>c If repeat imaging is needed, the permissible lag time will be extended by a maximum of an additional 14 days.

<sup>d Examined when considered necessary in unscheduled visit

<sup>e Patients who discontinued the study will be followed until the Week 26 visit.

be recorded using the 24-hour clock (e.g., 23:20, not 11:20 pm).

- 7.2.1 Screening (Visit 1)
  - Obtain written informed consent
  - Record demographic and medical history
  - Record the use of concomitant drug/therapy
  - Document occurrence of lumbar surgery
  - Verify conformance with entry criteria
  - Perform vital signs assessments (temperature, blood pressure, heart and respiration rate)
  - Perform physical examination
  - Perform neurological examination
  - Complete pain assessment (VAS)
  - Perform imaging tests (X-ray and MRI)
  - Obtain study entry laboratory specimens (blood for HIV; pregnancy [for women of childbearing potential]; and hematology, hepatic, and chemistry panels)

#### 7.2.2 Treatment Day 0 (Visit 2)

The following will be performed on the day of study drug administration (Day 0) before study drug administration:

- Enroll the patient if not done the day before
- Record concomitant drug and therapy information, including drugs or therapy used to treat an AE
- Record AEs and SAEs since previous visit
- Document occurrence of lumbar surgery
- Perform vital sign assessments (temperature, blood pressure, heart and respiration rate)
- Perform physical examination
- Complete pain assessment (VAS) and ODI
- Obtain blood specimen for serum anti-SI-6603 antibody
- Perform urine pregnancy test
- Administration of SI-6603

The following will be done after study drug administration:

Require patients to rest for at least 4 hours. During this resting period the patient's vital signs and general health status will be monitored. After patient monitoring, the Investigator will judge if the patient is ready for discharge based on observation and verification that there are no findings that negatively influence discharging the patient.

- Record concomitant drug and therapy information, including drugs or therapy used to treat an AE
- Record AEs and SAEs

• Perform vital sign assessments (temperature, blood pressure, heart and respiration rate)

#### 7.2.3 Evaluation Period, Week 1 (Visit 3)

- Complete pain assessment (VAS) and ODI
- Record concomitant drug and therapy information, including drugs or therapy used to treat an AE
- Record AEs and SAEs since previous visit
- Document occurrence of lumbar surgery
- Perform vital sign assessments (temperature, blood pressure, heart and respiration rate)
- Perform neurological examination
- Obtain laboratory specimens (blood for hematology, hepatic, and chemistry panels)

# 7.2.4 Evaluation Period, Week 6 (Visit 4)

- Complete pain assessment (VAS) and ODI
- Record concomitant drug and therapy information, including drugs or therapy used to treat an AE
- Record AEs and SAEs since previous visit
- Document occurrence of lumbar surgery
- Perform vital sign assessments (temperature, blood pressure, heart and respiration rate)
- Perform neurological examination
- Perform imaging tests (X-ray and MRI)
- Obtain laboratory specimens (blood for hematology, hepatic, and chemistry panels)

#### 7.2.5 Evaluation Period, Week 13 (Visit 5)

- Complete pain assessment (VAS) and ODI
- Record concomitant drug and therapy information, including drugs or therapy used to treat an AE
- Record AEs and SAEs since previous visit
- Document occurrence of lumbar surgery
- Perform vital sign assessments (temperature, blood pressure, heart and respiration rate)
- Perform neurological examination
- Perform imaging tests (X-ray and MRI)
- Obtain laboratory specimens (blood for hematology, hepatic, and chemistry panels)

• Obtain blood specimen for serum anti-SI-6603 antibody

#### 7.2.6 Evaluation Period, Week 26 (Visit 6)

- Complete pain assessment (VAS) and ODI
- Record concomitant drug and therapy information, including drugs or therapy used to treat an AE
- Record AEs and SAEs since previous visit
- Document occurrence of lumbar surgery
- Perform neurological examination
- Perform imaging tests (X-ray and MRI)
- Obtain blood specimen for serum anti-SI-6603 antibody

#### 7.2.7 Discontinuation Visit

- Complete pain assessment (VAS) and ODI
- Record concomitant drug and therapy information, including drugs or therapy used to treat an AE
- Record AEs and SAEs since previous visit
- Document occurrence of lumbar surgery
- Perform vital sign assessments (temperature, blood pressure, heart and respiration rate)
- Perform neurological examination
- Perform imaging tests (X-ray and MRI)
- Obtain laboratory specimens (blood for hematology, hepatic, and chemistry panels)
- Obtain blood specimen for serum anti-SI-6603 antibody

Patients who discontinue early from the study should, if possible, have a Discontinuation Visit. This visit should take place as soon as possible after it was learned that the patient will not be able to complete the study (see also Section 4.3).

# 8 STATISTICAL METHODS

The statistical considerations summarized in this section outline the plan for data analysis of this study.

Before database lock, a Statistical Analysis Plan (SAP) will be finalized, providing detailed methods for the analyses outlined below. The analyses specified in the SAP will be performed and the Clinical Study Report (CSR) will be prepared upon database lock. Any changes from the planned analyses will be described and justified in the final CSR.

#### 8.1 Study Patients

#### 8.1.1 Disposition of Patients

Patient disposition and reasons for discontinuation will be summarized for all enrolled patients.

#### 8.1.2 Analysis Sets

The following populations will be assessed:

- Safety: All patients who were treated with an investigational drug.
- Intent-to-Treat (ITT): All patients who were treated with an investigational drug.

If considered necessary, further populations may be defined in the SAP.

#### 8.2 General Considerations

Categorical variables will be summarized in a contingency table by the number and percentage of patients in each category. Continuous variables will be summarized by the number of observations, mean, standard deviation (SD), median, inter-quartile range, minimum, and maximum. Where data are collected over time, both the observed data and change from the Screening period (baseline) will be summarized at each time point. All eCRFs collected and derived data will be listed.

Methods for imputation of missing data and criteria for inclusion of patients in efficacy analyses will be specified.

All statistical tests will be performed 2-sided with a significance level of 5%, unless otherwise stated.

#### Analysis and Data Conventions:

Definition of baseline

For vital signs, laboratory tests, imaging procedures, neurological examinations, and ODI, the last valid assessment made before administration of investigational drug will be used as the baseline for all analyses of that parameter.

For the efficacy parameters of pain assessment measured by VAS, the baseline value of the worst leg pain and back pain over the past 24 hours (VAS) will be the VAS obtained on the day of enrollment (Day -1/Day 0).

#### Visit windows

All data collected during study follow-up will be displayed and analyzed according to the actual visit date in the eCRF. Assessments taken outside of protocol allowable windows will be displayed according to the eCRF assessment recorded by the Investigator.

#### Unscheduled assessments

Unscheduled assessments (laboratory data or vital signs associated with non-protocol clinical visits or obtained in investigating or managing AEs) will be included in listings, but not presented in the summary tables. If more than one laboratory value is available for a given visit, the last assessment will be used at the Screening visit, and the first valid observation will be used at all other post-baseline visits in summary tables and all observations will be presented in listings. It is noted that invalid laboratory data may not be used (from hemolyzed samples, mishandled samples, quantity not sufficient, or other conditions that would render values invalid).

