# Figure 1: Study Design

#### **3.2** Criteria for Evaluation of the Study

#### 3.2.1 Safety Endpoints

The following safety endpoints will be assessed:

- Occurrences of AEs
- Stability evaluation of vertebral bodies by X-ray at the times specified in the schedule of events
  - Translation of vertebral body
  - Vertebral body angle formed by flexion
- Changes from baseline in disc height (disc index) assessed by X-ray at the times specified in the schedule of events
- Changes of disc degeneration, vertebral body endplates, and adjacent bone marrow assessed by MRI at the times specified in the schedule of events
  - Modic classification
  - Pfirrmann classification
- Clinically significant change in vital signs at the times specified in the schedule of events
- Clinically significant change in clinical laboratory tests at the times specified in the schedule of events
- Serum anti-SI-6603 antibody at the times specified in the schedule of events
- Occurrence of post-treatment lumbar surgery other than surgery for lumbar disc herniation at the same level of the investigational drug administration

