# 8.6.2 Vital Signs

For body temperature, blood pressure, heart rate and respiration rate, descriptive statistics will be calculated at each time point.

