#### 8.6.3 Laboratory Tests

For laboratory data, descriptive statistics will be calculated for each time point.

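### Sections 8.6.2 and 8.6.3 plan no patient count for clinically significant laboratory or vital-sign change, and Section 8.2 keeps unscheduled values out of the tables those sections produce

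*Combined protocol and SAP*

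**What the plan says.** - **Endpoint.** Section 3.2.1 lists "Clinically significant change in clinical laboratory tests at the times specified in the schedule of events" and "Clinically significant change in vital signs at the times specified in the schedule of events". No criterion for clinical significance is given for either.
- **Planned analysis.** Section 8.6.3 reads in full: "For laboratory data, descriptive statistics will be calculated for each time point". Section 8.6.2 reads in full: "For body temperature, blood pressure, heart rate and respiration rate, descriptive statistics will be calculated at each time point". Under Section 8.2 the statistics for a continuous variable are the number of observations and "mean, standard deviation (SD), median, inter-quartile range, minimum, and maximum", for observed values and for change from baseline.
- **Synopsis.** The statistical paragraph plans AE incidence with a 95% CI and the same kind of analysis for other categorical safety endpoints.
- **Unscheduled values.** Section 8.2 says that laboratory and vital-sign values from non-protocol visits or "obtained in investigating or managing AEs) will be included in listings, but not presented in the summary tables".
- **Repeat laboratory values.** Where a visit has several, "the first valid observation will be used at all other post-baseline visits in summary tables and all observations will be presented in listings".
- **Schedule.** Table 3 and Section 7.2.6 include neither laboratory tests nor vital signs at Week 26. The last scheduled ones for a completer are at Week 13.

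**The concern.** The endpoint is a yes-or-no fact about a patient: did a clinically significant change occur? A by-visit mean, median or range does not answer that. If 8.6.2 and 8.6.3 are followed exactly, the laboratory and vital-sign section of the report contains no estimate of the endpoint that 3.2.1 names.

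The rule in 8.2 makes this worse. Samples taken because something has gone wrong are among the likeliest to be abnormal, and they are sent to listings. The schedule widens the gap, because tabulated laboratory and vital-sign data stop halfway through the 26-week follow-up for patients who complete.

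This matters because safety is the primary objective and Section 8.8 sizes the study to describe infrequent treatment-related events with exact intervals. Table 1 gives some reason to look at liver enzymes. ALT increased was reported in 8 of 269 SI-6603 patients and AST increased in 4 of 269, with no placebo entry for either (N=128).

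**Working it through.** **1. The other safety endpoints, side by side**

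| Endpoint | Section | Patient-level result planned | 95% CI |
|---|---|---|---|
| Anti-SI-6603 antibody | 8.6.4 | proportion positive | yes |
| Disc height | 8.6.5 | percentage by 30% threshold | yes |
| Posterior angle | 8.6.6 | percentage by 5° threshold | yes |
| Translation | 8.6.7 | percentage by 3 mm threshold | yes |
| Modic | 8.6.8 | new type, shift table | yes |
| Pfirrmann | 8.6.9 | grade increase, shift table | yes |
| Lumbar surgery | 8.6.10 | percentage | not stated |
| Vital signs | 8.6.2 | none | none |
| Laboratory tests | 8.6.3 | none | none |

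Only the last two lack a patient count. The synopsis statement therefore reaches the imaging and antibody endpoints in Section 8.6 but not these.

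**2. Time without tabulated values**

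For completers, follow-up after Week 13 is 26 − 13 = 13 weeks, and 13/26 = 50% of the period. Section 6.1.2 mentions blood drawn at evaluation-period visits in general terms, but it refers to Table 3 for timing, and Table 3 and 7.2.6 agree that Week 26 has none for these tests. Patients who discontinue do have both assessments at the discontinuation visit.

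**3. The plan's own precision figures**

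The Clopper-Pearson limits for x events in n patients are the 2.5% quantile of Beta(x, n − x + 1) and the 97.5% quantile of Beta(x + 1, n − x).
- 3/1000: 0.062% to 0.874%. Section 8.8 states 0.06% to 0.87%.
- 15/1000: 0.842% to 2.462%. Section 8.8 states 0.84% to 2.46%.

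Both reproduce and are not in dispute.

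**4. What by-visit statistics show (assumed values)**

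Suppose ALT rises from 25 to 200 U/L in 10 of 1000 patients at a scheduled visit.
- Visit mean: 10 × (200 − 25)/1000 = 1.75 U/L higher.
- Maximum: at least 200 U/L, whether 1 patient or 10 reached it.
- Patient incidence: 10/1000 = 1.0%, which 8.6.3 does not ask for.

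If the same values occur only at unscheduled assessments, the by-visit laboratory table does not change at all.

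**5. Effect of leaving unscheduled values out of an incidence (assumed values)**

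The documents give neither the rate of clinically significant change nor the share seen only off schedule. Assume 15 true cases in 1000 and let f be that share. Visible cases are k = 15 × (1 − f), rounded.

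| f | k | Incidence | Exact 95% CI |
|---|---|---|---|
| 0 | 15 | 1.5% | 0.84% to 2.46% |
| 25% | 11.25 → 11 | 1.1% | 0.55% to 1.96% |
| 50% | 7.5 → 8 | 0.8% | 0.35% to 1.57% |
| 75% | 3.75 → 4 | 0.4% | 0.11% to 1.02% |
| 100% | 0 | 0% | 0% to 0.37% |

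Adding an incidence to 8.6.2 and 8.6.3 without changing 8.2 would therefore repair only part of the problem.

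**The case against.** Three stronger readings are tempting, and the documents support none of them.

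- **A reader might infer that the worst values never reach any summary.** They can. Minimum and maximum are tabulated at each visit, so an extreme at a scheduled visit is shown. An abnormal laboratory finding can also be an AE (6.1.1.2), and 8.6.1 tabulates AEs by system organ class, preferred term and severity. If the 10 assumed ALT rises were recorded as AEs, the AE table would show 1.0%. What remains is narrower. The AE table counts an event without its value, and 6.1.1.2 sets AE thresholds for imaging findings but none for laboratory tests or vital signs, so capture rests on the investigator.
- **A reader might infer that no incidence is planned anywhere.** The synopsis does plan it for categorical safety endpoints, and clinically significant change is categorical. The defect is that 8.6.2 and 8.6.3 do not carry it out and no criterion is defined.
- **A reader might infer that tabulating the first valid repeat biases the tables toward normal.** That is not shown. If an abnormal result prompts the repeat, the rule keeps the abnormal one. It loses an extreme only when the later repeat is the worse value.

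Two further defences have weight. Section 3.2.1 ties the endpoint to scheduled times, so excluding unscheduled values fits its literal wording; but no incidence at scheduled times is planned in Section 8.6 either. Section 8 is an outline, and a SAP is to follow before database lock. That SAP is to detail the analyses outlined, however, and no patient count is outlined for these endpoints, while the exclusion in 8.2 is already a stated rule.

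The earlier data should not be pressed. Drug-related ALT and AST increases were 1 of 269 each. Drug-related neutrophil decrease was less frequent on SI-6603 (6/269, 2.2%) than on placebo (7/128, 5.5%), and the one severe case was at 2.5 U, not the 1.25 U used here.

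**Conclusion.** The point holds as an inconsistency that is cheap to correct. A listed safety endpoint has no patient count in the sections that analyse it, although the synopsis plans that kind of result and the imaging and antibody endpoints receive it. Extremes found only at unscheduled assessments, which for completers means any value after the Week 13 visit, reach listings or investigator-recorded AEs but no laboratory or vital-sign summary.

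The size cannot be derived from the documents. Under the assumption of 15 true cases in 1000, the shortfall in a scheduled-only incidence runs from 0.4 percentage points (1.5% to 1.1%) when a quarter of cases are seen only off schedule to the full 1.5 points when all are. Few off-schedule cases would mean little loss.

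The conclusion assumes that no separate SAP already supplies these summaries; none is in the text reviewed. It does not call into question the AE analysis in 8.6.1 or the intervals in 8.8.

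**What to change.** - **8.6.2 and 8.6.3:** add the number and percentage, with exact 95% CI, of patients with a clinically significant or treatment-emergent out-of-range change at any post-baseline assessment. Fix the criteria before database lock. State the denominator, for example patients with at least one post-baseline value, since 8.2 does not in general impute safety data.
- **8.6.3:** add a shift table from baseline to worst post-baseline value for each laboratory parameter.
- **8.2:** state that unscheduled and repeat values count toward these patient-level summaries and are excluded only from by-visit descriptive statistics.
- **3.2.1:** align the wording that ties these endpoints to scheduled times, so that the endpoint and its analysis cover the same assessments.

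The by-visit tables can stay as planned. The cost is some extra programming and agreement on criteria, and no new data collection. The trade-off is that reported abnormality rates may be slightly higher than from scheduled values alone.

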#### Missing data conventions

In general, data will not be imputed for safety analyses.

# 8.3 Demographics, Medical History, Baseline Characteristics, and Concomitant Medications

Demographic data and other baseline characteristics will be summarized by descriptive statistics with number of patients, mean, SD, median, inter-quartile range, minimum, and maximum. Categorical variables (e.g., sex and race) will be tabulated using frequency and percentage for each category of interest. Medical history and concomitant medication data will be provided in separate listings.

